## 5.2. Study Flow Chart

Procedures	Visit 1 	Visit 2 	Visit 3 	Visit 4 	Visit 5 	Visit 6  (EOT  / EOS  )
Name of Visit	Screening -35 – 0	Baseline Day 1	Week 2 Day 15	Week 4 Day 29	Week 8 Day 57	Week 12 Day 85
Visit window			± 3 days	± 3 days	± 3 days	± 4 days
Informed Consent	X					
Demographics	X					
Medical History/Previous Therapies	X	X				
Brief Physical Examination		X				X
Inclusion/Exclusion Criteria	X	X				
Urine Pregnancy Test 	X	X		X	X	X
IGA	X	X	X	X	X	X
Inflammatory Lesion Counts	X	X	X	X	X	X
Assessment of Eligibility		X				
Rosacea Erythema Assessment		X	X	X	X	X
Telangiectasia Assessment		X	X	X	X	X
Randomization		X				
Cutaneous Safety Assessment and Local Tolerability Assessments		X	X	X	X	X
Administer/ Review Patient Instructions		X	X	X	X	
Weigh Study Product		X		X	X	X
Study Product Dispensed		X 		X	X	
Provide Cleanser and Moisturizer/Sunscreen 		X				
Diary Card dispensed		X		X	X	
Study Product Collected				X	X	X
Diary Card collected				X	X	X
Patient Compliance Reviewed (Diary)			X	X	X	X
Concomitant Therapy and Medication History Reviewed	X	X	X	X	X	X
Adverse Events	X 	X	X	X	X	X
Photography (select site(s))		X	X	X	X	X
Complete PAPSS, PAPI and PGI-S 		X	X	X	X	X
Complete PGI-C, PGI-TS and PGI-SE 			X	X	X	X
Complete RosaQoL 		X				X

 If no washout is needed, Visits 1 and 2 may occur on the same day. If a washout is needed, Visit 2 must occur within one month 35 days of Visit 1.

 All visit dates are in reference to Baseline, e.g., Visit 5 occurs 8 weeks ± 3 days after Baseline Visit.

 All Week 12 procedures should be completed for Patients who terminate early.

 EOT – end of treatment

 EOS – end of study

 All women of childbearing potential

 Dispense one pump of test material at the Baseline Visit and dispense additional pump at Visit 4 and 5.

 Or study approved cleanser and moisturizer

 Adverse events after ICF is signed will be collected.

 PAPSS is Patient Assessment of Papulopustular rosacea Signs and Symptoms; PAPI is Patient Assessment of Papulopustular rosacea Impacts; PGI-S is Patient Global Impression of Symptom Severity. Questionnaires will be completed prior to PI assessment.

 In case Screening Visit and Baseline are on the same day, the PRO questionnaires should be completed prior to screening procedures.

 PGI-C is Patient Global Impression of Change; PGI-TS is Patient Global Impression of Treatment Satisfaction; PGI-SE is Patient Global Impression of Treatment Side-Effects. Questionnaires will be completed prior to PI assessment.

 RosaQoL is a Rosacea Quality of Life questionnaire.

## 6. LIST OF ABBREVIATIONS AND TERMS

AE(s)	Adverse Event(s)
ANCOVA	Analysis of Covariance
BPO	Benzoyl Peroxide
°C	Degrees Centigrade
CFR	Code of Federal Regulations
CRO	Contract Research Organization
E-BPO	Encapsulated Benzoyl Peroxide
eCRF	Electronic Case Report Form
FDA	Food and Drug Administration
g	Grams
cGCP	current Good Clinical Practice
h	hour(s)
IB	Investigator's Brochure
ICF	Informed Consent Form
ICH	International Conference on Harmonisation
IGA	Investigator's Global Assessment
IND	Investigational New Drug
IRB	Institutional Review Board
ITT	Intent-to-Treat
IWRS	Interactive Web Response System
MCMC	Markov Chain Monte Carlo
MedDRA	Medical Dictionary for Regulatory Activities
min	Minutes
mg	Milligram
NRS	Numerical Rating Scale
OTC	Over-the-Counter
PAPI	Patient Assessment of Papulopustular Rosacea Impacts
PAPSS	Patient Assessment of Papulopustular Rosacea Signs and Symptoms
PGI-C	Patient Global Impression of Change
PGI-S	Patient Global Impression of Symptom Severity
PGI-SE	Patient Global Impression of Treatment Side-Effects
PGI-TS	Patient Global Impression of Treatment Satisfaction
PI	Principal Investigator
PRO	Patient Reported Outcome

PP	Per Protocol
SAE	Serious Adverse Event
SOP	Standard Operating Procedure
VRS	Verbal Rating Scale

## 7. INTRODUCTION AND BACKGROUND

S5G4T-1 is an innovative topical formulation containing 5% encapsulated benzoyl peroxide (E-BPO) that Sol-Gel is developing for the treatment of rosacea. If approved, S5G4T-1 will be the first product containing E-BPO for the treatment of rosacea. Sol-Gel believes S5G4T-1 has the potential to be as tolerable as, and more effective than, currently marketed rosacea drugs.

Rosacea is a chronic and recurrent inflammatory dermatological disorder of unknown etiology. The disease is common, especially in fair-skinned people of Celtic and northern European heritage. The onset of the disorder is usually between the ages of 30 and 50. Early stages of the disease affect women more often than men at a ratio of 3 to 1 (Jansen and Plewig 1997 and McDonnell and Tomecki 2000). Rosacea usually starts as flushing and subtle redness on the cheeks, nose, chin or forehead. Alcohol, hot drinks, spicy foods, stress, sunlight and extreme heat or cold can trigger the onset of this disease. If left untreated, rosacea can slowly worsen over time. As the condition progresses, patients experience inflammatory lesions (papules and pustules), vivid erythema and telangiectasia. Patients may develop furuncles, cystic nodules, granulomas and tissue hypertrophy, sometimes leading to rhinophyma.

The first report on the treatment of rosacea with benzoyl peroxide as a single agent was described by in Montes *et al.* in 1983. In this limited study, 5% benzoyl peroxide, after 5 to 8 weeks of treatment, demonstrated superiority compared to control with respect to papules, pustules and erythema but not telangiectasia. The formulation was a basic formulation with benzoyl peroxide dissolved and delivered in acetone. Irritation and burning was reported in both groups, most likely due to the well-known effects of benzoyl peroxide.

More recently, Breneman *et al.* 2004 published the results of a study in collaboration with J. Leyden. This study was a double-blind, vehicle-controlled study, using a combination gel product of 5% benzoyl peroxide and 1% clindamycin to treat patients having moderate to severe rosacea. The most dramatic effect of the benzoyl peroxide/clindamycin treatment was on the reduction of papules and pustules. Side effects included the well-known effects of benzoyl peroxide, burning and itching.

Yamasaki *et al.* published a paper in 2007 which may explain why benzoyl peroxide potentially has a therapeutic benefit in the treatment of rosacea. The team reported that a protease that splits the antimicrobial peptide, cathelicidin, from its protein precursor is elevated in inflammatory rosacea. Cathelicidin subsequently induces the formation of the pro-inflammatory cytokine IL-8. It has also been previously reported that *Propionibacterium acnes* induces elevated levels of cathelicidin in the skin. These observations support the hypothesis that *P. acnes* has a major role in the etiology of rosacea, and provide a mechanistic understanding of why benzoyl peroxide may have a therapeutic benefit in the treatment of rosacea.

Rosacea is treated with both systemic and topical therapies. However, topical therapies are preferable because of side effects caused by the use of systemic therapies.

According to the U.S. National Rosacea Society, approximately 16 million people in the United States are affected by rosacea. According to a study commissioned by the Sponsor, approximately 4.8 million people in the United States experience subtype II symptoms and physicians estimate that only 20% of the U.S. rosacea population is treated. The topical drugs approved by the FDA to treat subtype II rosacea generated aggregate revenues of approximately \$392 million in the United States for the 12 months period ending June 30, 2017.

[REDACTED]

[REDACTED]

[REDACTED]

## 8. OBJECTIVE

- **The primary objective of this pivotal study is:**

1. To assess the efficacy and safety of S5G4T-1 compared to S5G4T-1 Vehicle when applied once daily for 12 weeks in patients with papulopustular rosacea.

The co-primary efficacy endpoints are to be evaluated using the following parameters:

- Proportion of patients with the primary measure of success “Clear” (0) or “Almost clear” (1) in the IGA relative to Baseline at Week 12.
- Absolute change in inflammatory lesion counts from baseline to Week 12.

- **The secondary objective of this pivotal study is:**

To demonstrate statistical superiority in efficacy of S5G4T-1 compared to the vehicle with regard to percent change from baseline.

The co-secondary efficacy endpoints are:

- Percent change in inflammatory lesion count from baseline to Week 12
- Absolute change in inflammatory lesion count from baseline to Week 8
- Proportion of patients with the primary measure of success “Clear” (0) or “Almost clear” (1) in the IGA relative to Baseline at Week 8
- Absolute change in inflammatory lesion count from baseline to Week 4
- Proportion of patients with the primary measure of success “Clear” (0) or “Almost clear” (1) in the IGA relative to Baseline at Week 4

- **The supportive objective of this pivotal study is:**

To determine the time required to observe improvement in the efficacy parameters associated with clearance of rosacea for S5G4T-1 compared to vehicle.

Supportive efficacy endpoints include the following:

- Percent change in inflammatory lesion count at Week 8
- Percent change in inflammatory lesion count at Week 4
- Mean change comparison in PAPSS item 1 (burning) between groups from Baseline to Weeks 4, 8 and 12
- Mean change comparison in PAPSS item 2 (itching) between groups from Baseline to Weeks 4, 8 and 12
- Mean change comparison in PAPSS item 3 (redness) between groups from Baseline to Weeks 4, 8 and 12
- Mean change comparison in PAPSS item 4 (bumps) between groups from Baseline to Weeks 4, 8 and 12 Rosacea erythema assessment at Week 12
- Telangiectasia assessment at Week 12
- The proportion of patients in treatment relative to control who report at least “minimally improved” as measured by the PGI-C at Week 12

- Mean change in the components of the PAPI score between groups from Baseline to Week 12
- Proportion of patients in the treatment relative to control achieving a three-point improvement in the components of the PAPI score from Baseline to Week 12
- Patient Global Impression of Symptom Severity (PGI-S) at Week 12
- Patient Global Impression of Treatment Satisfaction (PGI-TS) at Week 12.
- A set of cumulative distribution function (CDF) curves will be generated to allow for the evaluation of within-person change by treatment group. Specifically, 5 plots will be generated showing the change from baseline to Week 12 [and/or other, earlier time points if so desired] by the cumulative percent of subjects for each of the treatment arms (change on the x-axis will be expressed as absolute change) on:
  - PAPSS total scale scores;
  - PAPSS item 1 (burning) scores;
  - PAPSS item 2 (itching) scores;
  - PAPSS item 3 (redness) scores; and
  - PAPSS item 4 (bumps) scores

- **The safety objective of this pivotal study is:**

The safety objectives of this study are to determine the nature, severity and frequency of the adverse event rate, the Cutaneous Safety Assessment and the Local Tolerability Assessment of S5G4T-1 compared to the vehicle.

The safety endpoints to be assessed include the following:

- Adverse events (AEs), including serious adverse events (SAEs) occurring at any time during the trial.
- Investigator Cutaneous Safety Assessment and Local Tolerability Assessments score at any time during the trial.

## **9. ETHICS**

This study will be conducted in compliance with FDA regulations, the ethical principles of the Declaration of Helsinki, and the current ICH- Good Clinical Practice (cGCP) guidelines. The investigator and all study staff will conduct the study in compliance with this protocol.

The protocol, informed consent documents, any information provided to patients, recruitment advertisements and any amendments to these items will have Institutional Review Board (IRB) approval prior to their use in the study. Voluntary informed consent will be given by every patient prior to the initiation of any study related procedures. The rights, safety and well-being of the study patients are the most important considerations and prevail over the interests of science and society.

All personnel involved in the conduct of this study must be qualified by education, training and experience to perform their assigned responsibilities.

## **10. INSTITUTIONAL REVIEW BOARD (IRB) AND INFORMED CONSENT**

Before study initiation, this protocol, the investigational brochure for encapsulated benzoyl peroxide cream (E-BPO) in the treatment of rosacea, the informed consent form, and any other written information given to patients, and any advertisement for patient recruitment must have IRB approval. The investigator will submit documentation of the IRB approval to the Sponsor, Sol-Gel Technologies Ltd., or their CRO designee.

The IRB-approved consent form must include all elements required by FDA, state, and local regulations, and may include appropriate additional elements.

The investigator/designee will explain the study to each potential patient and the patient must indicate voluntary consent by signing and dating the approved informed consent form. The consent process will be conducted prior to the start of any study-related procedures including a washout period. The investigator must provide the patient with a copy of the consent form, in a language the patient understands.

The investigator will maintain documentation that informed consent was obtained prior to the initiation of any study-related procedures.

## 11. OVERALL STUDY DESIGN

This study will be a randomized, double-blind, multicenter, parallel group, active- and vehicle-controlled pivotal study of the efficacy, and safety of S5G4T-1 and its vehicle for the treatment of papulopustular rosacea for 12 weeks. Approximately 350 patients with moderate to severe rosacea (rated 3 or 4 on the 5-point IGA scale) will be enrolled at up to 28 sites. Patients in this randomized, double-blind, vehicle-controlled, parallel-group multi-center study will be randomly assigned in a 2:1 ratio to S5G4T-1 or vehicle, respectively. Subjects with severe rosacea who are appropriate for systemic treatment need to be counseled regarding their treatment options by the Principal Investigator.

Patients will receive once daily treatment with S5G4T-1 or vehicle cream for 12 weeks. After the screening period, qualified patients will be randomly assigned at the Baseline visit and treated for 12 weeks. Efficacy assessments will include facial inflammatory lesion counts and IGA assessment ranging from 0 (Clear) to 4 (Severe). Investigators will be provided with instructions for lesion counts to ensure consistency of procedure. Patient reported outcomes (PRO) will be assessed with the PAPSS (Patient Assessment of Papulopustular rosacea Signs and Symptoms), PAPI (Patient Assessment of Papulopustular rosacea Impacts) and PGI-S (Patient Global Impression of Symptom Severity) that will be administered at Baseline, Weeks 2, 4, 8 and 12, or at early termination. In addition, the PGI-C (Patient Global Impression of Change), PGI-TS (Patient Global Impression of Treatments Satisfaction) and PGI-SE (Patient Global Impression of Treatments Side Effects) will be administered at Weeks 2, 4, 8 and 12, or at early termination [FDA Guidance 2009]. Rosacea Quality of Life (RosaQoL) questionnaire will be administered at Baseline, and Week 12, or at early termination. Safety will be assessed at all visits and will include monitoring local and systemic adverse events (AEs); the investigator Cutaneous Safety Assessment rating of erythema, dryness and scaling and Local Tolerability Assessments rating of itching and burning/stinging on a scale ranging from 0 (None) to 3 (Severe).

Patients will return to centers for IGA, lesion counts, PRO questionnaire, , Investigator Cutaneous Safety Assessment and Local Tolerability Assessments at Weeks 2, 4, 8 and 12. At Week 12 (or at the early termination visit) patients will be asked to complete RosaQoL questionnaire. Adverse events and concomitant medications will be assessed throughout the treatment period. A urine pregnancy test is required at Visit 1, 2, 4, 5 and 6 for all females of child-bearing potential.

Clinical Evaluations will be performed at:

- Visit 1/Screening
- Visit 2/Baseline, Day 1
- Visit 3/Week 2, Day 15 ( $\pm$  3 Days)
- Visit 4/Week 4, Day 29 ( $\pm$  3 Days)
- Visit 5/Week 8, Day 57 ( $\pm$  3 Days)
- Visit 6/Week 12, Day 85 ( $\pm$  4 Days)/End of Treatment)

## 12. STUDY POPULATION

### 12.1. Randomization and Blinding

It is planned that approximately 350 patients who meet the inclusion/exclusion criteria will be enrolled in this study at up to 28 U.S. study sites. Patients will be at least 18 years of age and older, of either gender. Efforts will be made to enroll patients ages matching the target study population.

The study product will be administered in a double-blinded fashion, i.e., the treatment assignment will not be known to the patient, to study personnel, or Sol-Gel and its representatives. Patients will be instructed not to discuss the study product with the study personnel. Patients will be randomly assigned in a 2:1 ratio as follows:

- E-BPO Cream, 5% (S5G4T-1) (234 patients)
- Vehicle Cream (S5G4T-2) (117 patients)

Each patient who signs an informed consent, meets inclusion/exclusion criteria, and successfully completes the screening procedures, will be enrolled in the study. The patient randomization schedule will be a permuted block design stratified by investigational site. Blocks will be composed of 3 treatment assignments in a ratio of 2:1 study product and vehicle, respectively. Complete blocks from the randomization schedule will be allocated to investigational sites as they randomize patients to maintain the randomization ratio of 2:1 study product and vehicle, respectively.

Additionally, the staff involved in data management and statistical evaluation will remain blinded until identification of the per protocol population is finished and a database lock memo is issued.

The randomization schedule and treatment code will not be revealed to the patients, study personnel, Sol-Gel or its representatives until after the database lock, except to the Medical Monitor or Principal Investigator for an emergency. Access to the randomization list will be maintained by and limited to the unblinded Biostatistician and the designated personnel directly responsible for labeling of study materials. The Medical Monitor will not have access to the randomization list, but may determine that unblinding one or all patients may be necessary in the case that the safety of study patients is at risk. In an emergency, the study blind may be broken only if:

- In the opinion of the Medical Monitor and/or the PI, it is in the patient's best interest to do so
- Knowledge of the treatment will alter the clinical management of the patient

In the case of an emergency that requires unblinding, the Investigator can request to unblind the patient without prior contact with the Medical Monitor although follow-up between the Investigator and Medical Monitor must occur so that all parties are aware of the unblinding. Although it is recommended that the Investigator contact the Medical Monitor prior to unblinding any patient, in instances where this is not feasible or advisable the PI may directly access the patient's treatment assignment. In all situations, the Interactive Web Response System (IWRS) will be used to obtain treatment assignment information with limited access to only the above-designated individuals, and any unblinding will be documented as a protocol deviation.

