### 13.4. Assignment of Randomization

The patient randomization schedule will be a permuted block design stratified by investigational site. Blocks will be composed of 3 treatment assignments in a ratio of 2:1 study product and vehicle, respectively. Complete blocks from the randomization schedule will be allocated to investigational sites as they randomize patients. Patients will be randomized through the IWRS and assigned a unique randomization ID indicating treatment group. The study product supplies will be packed in 4 pumps per kit and will be numbered in a scrambled randomized method. The kits will be dispensed by the IWRS according to the randomized treatment group.

The first supplied pump in each kit is marked A (e.g. number of pump within a kit is XXXXA), at Visit 4/ Week 4 the patient will return the pump and will be dispensed with the next pump which is marked B. At Visit 5/ Week 8, the patient will return the pump and will be dispensed with a pump marked C. Pump marked as D may be dispensed to patients who lost/damaged/ran-out of study product.

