### 18.3. Study Products Packaging and Labeling

The study product (Encapsulated Benzoyl Peroxide Cream, 5%), S5G4T-1, and placebo for the study product (Vehicle Cream), S5G4T-2, will be packaged and labeled in 55-g airless pump. At the first 12 weeks of treatment, a double-blind technique will be used. In order to maintain the blind, the study product and vehicle will be supplied in identically-appearing labeled pump cartons. Neither the patient nor the investigational staff (sponsor, investigator, and evaluators) will know which treatment a patient is receiving.

The study products will be shipped to sites in blocks of three (3) products to keep ratio 2:1 between study product and vehicle. The study products will be labeled with the following:

- Protocol Number

- Patient Number
- Kit Number
- Pump Number
- Patient Initials
- Dispense Date
- Dispenser Initials
- Contains: one (1) pump of S5G4T-1 (Encapsulated Benzoyl Peroxide) Cream, 5% or its Vehicle Cream, 55 g
- Directions for use: Apply as directed, for topical use only.
- Storage conditions “Store at Room Temperature 20 to 25°C (68 to 77°F). Excursions permitted between 15 to 30°C (59 to 86°F).”
- Keep container tightly closed.
- Do not freeze and do not refrigerate.
- Keep out of reach of children.
- Study product warning. “Caution: New Drug - Limited by Federal Law to Investigational Use”
- Sponsor Information

Each Study Product Kit Box will contain four (4) pumps and will carry a two-part label with a perforation. The tear-off section of the label will be attached to the study product dispensing log at the time the study product is dispensed. The other label part must remain attached to the box. Both label parts will have spaces to enter the patient’s initials, date dispensed, dispenser’s initials. The constant label part shows:

- Protocol Number
- Patient Number
- Patient Initials
- Kit Number
- Randomization Date
- Contains: four (4) pumps of Encapsulated Benzoyl Peroxide (E-BPO) Cream, 5% or its Vehicle Cream, 55 g.
- Directions for use: Apply as directed, for topical use only.
- Storage conditions “Store at Room Temperature 20 to 25°C (68 to 77°F). Excursions permitted between 15 to 30°C (59 to 86°F).”
- Keep container tightly closed.
- Do not freeze and do not refrigerate.
- Keep out of reach of children.
- Study product warning. “Caution: New Drug - Limited by Federal Law to Investigational Use”
- Sponsor Information

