Pump usage will be demonstrated by the site personnel on a sample pump at the clinic to help assure the patient understands the procedure. The patient will be provided a set of instructions ([Appendix 1](#)) that includes study reminders and restrictions as described in this protocol. Patients will be instructed to bring the study product to each visit and to not apply study product one hour prior to the study visit. Patients should be instructed to store the study product at room temperature, not in the refrigerator or freezer and informed that the test article may bleach colored fabric.

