### **20.4. Required Study Documents**

The investigator must provide the following documents to Sponsor or CRO designee before any patients are enrolled and/or study product may be shipped to the study site:

- The signed INVESTIGATOR PROTOCOL ACKNOWLEDGEMENT page from the Sponsor and IRB approved protocol.
- Documentation of IRB approval of the protocol, informed consent form, any other written information provided to patients and any recruitment advertisements.
- A copy of the IRB approved informed consent form
- A current IRB assurance number and/or a membership roster.
- A completed, signed and dated Form FDA 1572.
- The appropriate financial disclosure documentation.
- A current signed and dated curriculum vitae and a copy of the current medical license for the investigator and sub-investigators listed on the Form FDA 1572.
- The signed agreement between the investigator and Sponsor, or designee, and related financial information for the study (this file is confidential and currently FDA has no authority to review this information. Keep this information in a separate file).

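### Sites are told that randomization uses a fixed block of 3 (2:1) within site, so a known vehicle patient reveals the block-mates; vary the block length and withhold it

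*Protocol*

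**What the plan says.** Protocol 12.1 sets out the method: "The patient randomization schedule will be a permuted block design stratified by investigational site". The next sentence fixes the block: "Blocks will be composed of 3 treatment assignments in a ratio of 2:1 study product and vehicle, respectively". Section 13.4 repeats both and adds "Complete blocks from the randomization schedule will be allocated to investigational sites as they randomize patients". Section 18.3 ties supply to the same unit: "The study products will be shipped to sites in blocks of three (3) products to keep ratio 2:1 between study product and vehicle". No second block length appears anywhere, and no text says that the length is kept from sites.

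Investigators hold this document. Among the papers that they must return, Section 20.4 lists "The signed INVESTIGATOR PROTOCOL ACKNOWLEDGEMENT page from the Sponsor and IRB approved protocol".

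The SAP (6.1.2 and 6.1.3) describes the IWRS, the 2:1 ratio and the restricted list. It gives no block length, so it leaves the protocol's rule as it stands.

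Protocol 12.1 also lets the principal investigator obtain one patient's assignment through the IWRS in an emergency, without contacting the Medical Monitor first. Section 13.2 names unblinding as a possible reason for withdrawing that patient. Nothing addresses the other patients in the same block.

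**The concern.** Complete blocks are used within one site, so the site's randomized patients 1 to 3, 4 to 6 and so on form the blocks. Staff who keep a simple log of randomization order know the boundaries. Learning that one patient is on vehicle then tells them what the other two are receiving.

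This matters because of how efficacy is measured. The IGA and the lesion counts are both made by site evaluators (Protocol 14, 14.1 and 14.2). Section 15 says that photographs play no part in efficacy assessment, and no independent reader is described. Knowing a patient's treatment by Week 12 is enough to colour a rating; the evaluator need not have predicted it at enrolment. Some room for selective enrolment exists as well, because exclusion 22 rests on investigator opinion and the site schedules Baseline after screening.

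**Working it through.** **Inputs.** Block of 3 with 2 active and 1 vehicle, stratified by site, complete blocks per site (Protocol 12.1 and 13.4). Planned arms of 234 and 117, and up to 28 sites (Protocol 12.1).

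**The plan's own allocation.** 117 blocks × 2 = 234 active and 117 blocks × 1 = 117 vehicle, 351 in total. This reproduces the stated arms. At 28 sites that is 351/28 ≈ 12.5 patients, or 12.5/3 ≈ 4.2 blocks, per site.

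**One vehicle patient known.** In a block of length b with v = b/3 vehicle assignments, the probability that a given block-mate is active is (b − v)/(b − 1), against a prior of 2/3 = 0.667.

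| Block length | Calculation | Probability that block-mate is active |
|---|---|---|
| 3 | 2/2 | 1.00 |
| 6 | 4/5 | 0.80 |
| 9 | 6/8 | 0.75 |

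**One active patient known, block of 3.** One active and one vehicle assignment remain, so each block-mate is active with probability 1/2. Two known active patients are needed to fix the third as vehicle.

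**Worst case: all earlier assignments in the block known.** Count the positions that are certain before they are assigned, over the three possible orders (A = active, V = vehicle):
- AAV: position 3 only, 1.
- AVA: position 3 only, 1.
- VAA: positions 2 and 3, 2.

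The total is 4 of 9 positions, or 44.4%. Three of the four are third positions, where both earlier assignments must be known. The same enumeration gives 13/45 = 28.9% for a fixed block of 6 and 3/14 = 21.4% for a fixed block of 9. Those two figures do not describe a mix of lengths.

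**A mix of 3 and 6.** Assume that each block is equally likely to be 3 or 6 and that the length is not disclosed. A vehicle patient then falls in a block of 3 with weight 1/3 and in a block of 6 with weight 2/3, because a block of 6 has two vehicle assignments and a block of 3 has one. The average probability that a block-mate is active is 1/3 × 1.00 + 2/3 × 0.80 ≈ 0.87. The site also no longer knows who the block-mates are.

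**Cost in balance.** In an unfinished block of 3, the vehicle count can differ from its 2:1 expectation by at most 2/3 of a patient (first patient V: 1 − 1/3; or first two A: 2/3 − 0). In an unfinished block of 6 the largest difference is 4/3 (first two V: 2 − 2/3; or first four A: 4/3 − 0).

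**The case against.** The tempting inference is that the product's visible effects will expose the vehicle patients. The documents do not support it. Patients are "informed that the test article may bleach colored fabric", and Protocol 12.5 lists dryness, burning, itching and scaling as possible reactions. These cues suggest active treatment, and one known active patient fixes neither block-mate. Vehicle would have to be read from an absence of cues, which is weak evidence. Burning and itching are also scored at Baseline, the bleaching warning goes to every patient, and patients are told not to discuss the product with staff. SAP Section 4 reports that all three Phase 2 formulations were well tolerated. This part of the objection stands: clinical signs are a poor route to the certain inference.

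The protocol also has real safeguards. Kits "will be numbered in a scrambled randomized method" and the IWRS dispenses them. Cartons look the same, the list is restricted, and any unblinding is recorded as a deviation. Shipment in threes does not by itself mean dispensing in threes. These measures prevent decoding from labels or from the list, but they do not hide the order in which a site randomized its patients.

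Enrolment is mostly driven by criteria: Section 12.1 says that consenting patients who meet them and complete screening are enrolled. Since the first post-baseline visit is Day 15, recognition at a visit can affect selection only if the next patient in the block enrols later. Selective enrolment is therefore the weaker route and biased rating the more plausible one.

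Finally, short blocks have a purpose. SAP 8.1.7 aims for at least 10 active and 5 vehicle patients per investigator, while the planned average is about 12.5 patients in all, so keeping the ratio tight at small sites has value.

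**Conclusion.** The point holds as a weakness in the protection of the blind that is cheap to reduce. It is a design choice, not an error or a contradiction. With a disclosed, fixed, site-specific block of 3, knowledge of one vehicle patient raises the probability that a block-mate is active from 0.667 to 1.00. Emergency unblinding is the one route that gives this knowledge with certainty.

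Two stronger statements should not be made. The first is that 44% of assignments are predictable. That figure is a ceiling, which requires every earlier assignment in the block to be known before the next patient is randomized. The second is that unblinding one vehicle patient automatically unblinds two others. The inference is open only to someone who sees the result and tracks the site's order, and a site's last block may be unfinished (at most 28 such blocks), so fewer than two block-mates may exist.

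The documents give no rate of guessing, recognition or unblinding. The number of patients affected and the bias in either co-primary endpoint therefore cannot be computed.

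**What to change.** 1. For blocks not yet allocated, generate the schedule with randomly varying lengths within site, for example 3 and 6.
2. Delete the block length from Protocol 12.1, 13.4 and 18.3, and hold it only in a randomization specification restricted to the unblinded statistician and the other designated unblinded staff.
3. Stop tying kit shipments to block boundaries. The IWRS makes every assignment, so sites do not need the block length to run the trial.

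Predictability is reduced but not removed: about 0.87 under the assumed equal mix, still above 0.667, with boundaries no longer known.

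The cost is a new schedule file, a revised supply rule, and a protocol amendment needing IRB approval (Protocol 20.2). Within-site imbalance rises slightly when a block of 6 is left incomplete, by up to 4/3 of a vehicle patient against 2/3 now, at sites averaging about 12.5 patients. The change cannot affect blocks already used. Nor can it recall a block length that sites have already read; SAP Section 2 lists protocol versions up to 4.0 as issued.
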